2.1.2. Primary evaluation criterion

- Haemoglobin level on day 5 post-operatively (considered the post-operative haemoglobin reference level in this study)
 - In the case of patients who received a transfusion postoperatively, the reference haemoglobin level will be the haemoglobin level at the end of hospitalisation
- Change in the Activities of Daily Living (ADL) score pre-fracture and 6 months post-operatively.
A loss of independence will be defined as a decrease of one point or more in the ADL.

The reference value for haemoglobin levels was arbitrarily set at 5 days post-operatively. This is because haemoglobin levels recorded in A&E or on admission to the ward prior to surgery, or immediately post-operatively, may be influenced by factors other than isolated anaemia. Dehydration, present in the emergency department or on admission to the ward before the operation, corrected preoperatively, and postoperative haemodilution due to fluid replacement, cause the haemoglobin level to vary without there being any real deglobulation. We therefore postulate that the haemoglobin level on the 5th postoperative day can serve as a reference.

Confounding factors collected

All confounding factors related to loss of autonomy will be collected:

- Transfusion and number of red blood cell concentrates received

The indication for transfusion is at the discretion of the prescriber. However, it is generally accepted to transfuse patients with haemoglobin levels below 8 g/dL, or below 10 g/dL in cases of ischaemic heart disease or poor clinical tolerance.

- Age
- Gender
- Height, weight, Body Mass Index (BMI) calculation
- Screening for past or present higher brain function disorders
- Screening for major sensory disorders
- Screening for depressive symptoms: Mini Geriatric Depression Scale (MiniGDS)
- Comorbidities assessed using the Cumulative Illness Rating Scale - Geriatrics (CIRS-G)
- ASA score
- Number of medications (per class) taken by the patient (anticoagulants, antiplatelet agents, NSAIDs, anti-osteoporotic drugs, analgesics)

- Lifestyle and living environment
- Severe fractures before and after inclusion
- Other falls during the year
- Protein-energy malnutrition
- Iron deficiency (ferritin < 30 µg/L or CRP > 20 mg/L associated with a transferrin saturation coefficient < 15%)
- Recurrence of falls at 1, 3 and 6 months post-op

2.2. *SECONDARY OBJECTIVES AND EVALUATION CRITERIA*

2.2.1. *Secondary objectives*

The secondary objectives are to analyse:

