- the influence of post-operative anaemia:
 - on independence in elderly patients who have undergone surgery for a fracture of the upper end of the femur upon discharge from hospital, at 1 month and 3 months post-operatively
 - on mortality 6 months after surgery
- the progression of post-operative anaemia

2.2.2. *Secondary evaluation criteria*

- Lowest postoperative haemoglobin level recorded on admission to the emergency department, on admission to the ward, on D0 (day of surgery), D1, D3, D5, D10 and D15 (postoperative days).
The severity of anaemia will be defined as follows:
 - greater than 12 g/dL,
 - less than or equal to 12 g/L
 - less than or equal to 8 g/L
 - less than 8 g/dL (and therefore requiring a transfusion)
- Assessment of Activities of Daily Living (ADL): pre-fracture, on day 5 post-operative (or on discharge from hospital if discharged before day 5) at 1 month, 3 months and 6 months post-operative.
- Assessment of instrumental Activities of Daily Living (IADL): pre-fracture, at 1 month, 3 months and 6 months post-operative.
Loss of independence will be defined as a decrease of one point or more in the ADL and/or IADL.
- Vital status at 6 months post-operatively

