Search for late post-operative complications: infection requiring antibiotic treatment (surgical site, pulmonary, urinary, skin, other), acute urinary retention requiring urinary catheterisation, dislocation/loosening of prosthesis, cardiovascular/neurological complications, reoperation.

Record of recurrent falls or fractures New

hospitalisation and reason for hospitalisation

Number of medications (by class) taken by the patient (anti-osteoporotic, analgesic) Vital status record

STUDY TIMELINE					
Actions	D Arrival in the orthopaedic surgery department (day of surgery)	From D1 to D4 post-op.	Day 5 post-op**	End of hospitalisation	M1, M3 and M6 post-op (+/- 15 days) Telephone follow-up
Information for patient/family/trusted relative Collection of non-objection form	X *				
ADL	X ¹		X		X
IADL	X ¹				X
CAS	X ¹	X (from D1 to D3)	X		X
HandGrip Test			X		
ASA score/CIRS-G score/MiniGDS score	X				
Confusion screening (CAM)		X (daily – up to day 10 if patient is still hospitalised)			
Screening for previous or current higher brain function disorders	X			X	
Check for major sensory disorders	X				
Haemoglobin	X	X (D1, D3, D5, D10, D15)			
NFS, CRP, albumin, ferritin, transferrin saturation coefficient, vitamins B12, folates and vitamin D	X				
Information about the procedure ²	X				
Post-operative complications		X (daily) ³			X ⁴
Fractures/falls	X (fractures)	X (daily)			X
Length of hospital stay/Discharge status				X	
Re-hospitalisation and reason					X
Concomitant treatments	X ⁵	X (End of hospitalisation) ⁵			X(M6) ⁶
Vital status		X	X	X	X

* Can be performed up to 48 hours after arrival at the department

** Five days after surgery or upon discharge from hospital if this occurs before five days

¹: Information relating to the week preceding the operation

² : Time of surgery, type of fracture, surgical procedure, type of anaesthesia, weight-bearing authorisation, transfusion, number of red blood cell units received

³ : Post-operative infection requiring antibiotic treatment (surgical site/pulmonary/urinary/skin/other), acute urinary retention requiring urinary catheterisation, dislocation/loosening of prosthesis, iron and/or vitamin deficiencies, transfusion, number of packed red blood cell units received, cardiovascular/neurological complications, post-operative bleeding (including local and digestive), reoperation, haematomas,

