5.2.1. Description of methods planned planned, including the schedule for planned interim analyses

All variables collected will be described by minimum, maximum, quartiles, mean and standard deviation for quantitative variables and by number and percentage of each modality for qualitative variables.

Analysis of the primary endpoint:

The relationship between loss of independence at 6 months and post-operative anaemia will be analysed using a logistic model. If a link is found, a multivariate analysis will be performed to confirm the independence of the anaemia/independence relationship. To do this, all potential confounding factors will be tested in a univariate analysis. Factors associated with a p value <0.20 will be retained in the multivariate model.

Analysis of secondary criteria:

- The analysis of the relationship between loss of autonomy on day 5 (or on discharge from hospital if discharged before day 5), at 1 and 3 months, and post-operative anaemia will be performed using the same method as for the primary endpoint.
- The 6-month mortality rate will be estimated with its 95% confidence interval using the Kaplan-Meier method.

The association between anaemia and mortality at 6 months will be studied using a Cox proportional hazards model in order to take confounding factors into account.

- The progression of post-operative anaemia (D0 to D15) will be described graphically.

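### Independence at discharge is answered with day-5 ADL, and in some post-operatively transfused patients the haemoglobin exposure is read after that ADL

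*Combined protocol and SAP*

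**What the plan says.** **Time point of the outcome.** The secondary objective in section 2.2.1 is the influence of post-operative anaemia on independence "upon discharge from hospital, at 1 month and 3 months post-operatively". The matching criterion in section 2.2.2 takes the early ADL "on day 5 post-operative (or on discharge from hospital if discharged before day 5". The footnote to the study timeline in section 4.1 defines that visit as "Five days after surgery or upon discharge from hospital if this occurs before five days", and section 4.3 agrees. The analysis in section 5.2.1 has the same timing: "The analysis of the relationship between loss of autonomy on day 5 (or on discharge from hospital if discharged before day 5". The end-of-hospitalisation procedures in section 4.1 (item c) do not include ADL, and the timeline has no ADL mark in that column.

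**Exposure.** Section 2.1.2 makes the day-5 haemoglobin the value "considered the post-operative haemoglobin reference level in this study". For patients transfused post-operatively it substitutes another: "the reference haemoglobin level will be the haemoglobin level at the end of hospitalisation". Section 5.2.1 says that the analysis of early loss of autonomy against "post-operative anaemia will be performed using the same method as for the primary endpoint", and names no different haemoglobin value for it.

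**The concern.** The objective asks how anaemia relates to independence when the patient leaves hospital. For anyone who stays past day 5, the data to answer that are never collected.

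The second problem is time order. Replacing the day-5 haemoglobin by the end-of-stay value does no harm to order when the outcome is at 6 months. Carried over to a day-5 outcome, the same rule can pair a day-5 ADL with a haemoglobin taken days later. Two statements in the protocol make this more than a formality. Section 2.1.2 gives poor clinical tolerance as one accepted ground for transfusing at a higher haemoglobin, and section 1.1 says that anaemia limits mobilisation on the ward. Poor early function could therefore influence transfusion, and through it the end-of-stay haemoglobin. A transfusion after day 5 would also change the exposure assigned to an ADL already recorded. An analysis meant to show the influence of anaemia on function should not let the exposure follow the outcome.

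**Working it through.** The documents give no figure on this point. Their one sample-size figure, 255 in section 5.2.2, is reproduced by 210 × 1.5 × 0.9 × 0.9 = 255.15 (or nearly by 320 × 0.80 = 256), but the point does not depend on it. The check is a comparison of dates.

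**Step 1: are stays beyond day 5 foreseen?** Yes. Section 4.1 plans daily confusion screening to day 10 for patients still in hospital.

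**Step 2: when is haemoglobin taken?** Section 4.1 schedules D1, D3, D5, D10 and D15, with a tolerance of 2 days either way. No separate sample is scheduled at the end of hospitalisation. The end-of-stay value is therefore the last one available in hospital. The D10 window opens at 10 − 2 = day 8.

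**Step 3: which comes first in the day-5 analysis?**
- Not transfused post-operatively, in hospital on day 5: ADL and haemoglobin are both nominally day 5.
- Transfused post-operatively, discharged on or before day 5: ADL and end-of-stay haemoglobin fall at about the same time.
- Transfused post-operatively, discharged after day 5 but before the D10 window, with no unscheduled sample: the last in-hospital value is the D5 one, so the order is not reversed.
- Transfused post-operatively, with an in-hospital haemoglobin after the day-5 ADL (a scheduled D10 or D15 sample, or an unscheduled one): the exposure is read after the outcome.

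Only the last group is reversed. The missing discharge ADL concerns everyone discharged after day 5, transfused or not.

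**Step 4: how large is the reversed group?** It cannot be computed, because the documents give no transfusion rate and no length of stay. For scale only, assume that a share t = 20% to 50% is transfused post-operatively and that a share s = 30% to 90% of those stay past day 5. Then t × s runs from 0.20 × 0.30 = 6% to 0.50 × 0.90 = 45%, or 255 × 0.06 ≈ 15 to 255 × 0.45 ≈ 115 patients. This overstates the group, since it counts everyone in the third case above. Also, 255 is the number analysable at 6 months, not the number with a day-5 ADL.

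**Step 5: does it move the estimate?** A crude simulation assumed day-5 haemoglobin with mean 10 and SD 1.3 g/dL, and a true odds ratio of 1/1.3 = 0.77 per g/dL. Patients below 8, 9 or 9.5 g/dL were transfused (6%, 22% or 35%). In 30%, 60% or 90% of them the value was replaced by one higher by 1.7 g/dL on average (SD 0.6). The fitted odds ratio stayed between 0.76 and 0.78. The simulation had no path from early function to transfusion, so it shows only the effect of substituting later values. It does not test the reverse path.

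**The case against.** **The wording mismatch is small.** Sections 2.2.2, 4.1 (text and timeline), 4.3 and 5.2.1 all agree on day 5 or earlier discharge. A reader might infer that the result will be reported as independence at discharge. The documents do not support that: the analysis text itself says day 5, so a result produced under it would carry the right label. This stands, and it reduces the first half to one phrase in the objective. That phrase still promises something not collected for longer stays.

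**The reversal is narrower than it looks.** A reader might infer that it touches every patient transfused on the ward. It does not. It needs a post-operative transfusion and an in-hospital haemoglobin later than the ADL, which means a stay reaching about the D10 window or an unscheduled sample. The rule in section 2.1.2 also names only post-operative transfusion, which section 4.4 separates from transfusion before surgery or in the recovery room.

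**The exposure is inferred.** Section 5.2.1 says only post-operative anaemia, and the phrase "will be performed using the same method as for the primary endpoint" could be read as meaning the logistic model alone. Section 2.2.2 lists another haemoglobin measure, the lowest value. This is a fair point, but section 2.1.2 declares its reference level for the whole study. The lowest-value list also runs to D10 and D15, so a late minimum would again post-date the day-5 ADL. Neither reading secures the order.

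**Conclusion.** The point holds in limited form. The discharge objective in section 2.2.1 is not answered for patients who leave after day 5. The day-5 analysis, on the most natural reading of sections 2.1.2 and 5.2.1, dates the exposure after the outcome in post-operatively transfused patients who have a later in-hospital haemoglobin.

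The size of that group is unknown. A reader might try to derive it from the cited haemoglobin figures by counting patients below 8 g/dL. The documents do not support this: section 1.1 gives no cut-off for its 93.0% with post-operative anaemia, section 2.1.2 leaves transfusion to the prescriber and describes a higher threshold for some patients, and length of stay, which decides whether any reversal occurs, is missing.

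Nor do the documents support a claim of serious bias. None has been shown, although a path from function to transfusion has not been ruled out. The 1-, 3- and 6-month outcomes normally come after the end-of-stay haemoglobin and are unaffected, unless a stay runs past 1 month. The correction is worth making before analysis because it is cheap and the order of exposure and outcome should not be left to inference.

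**What to change.** 1. In section 2.2.1, word the early objective as independence on day 5, or at discharge if earlier, to match the rest of the protocol.
2. In section 5.2.1, state the exposure for this analysis: in all patients, only haemoglobin measured on or before the day of the ADL, that is the D5 value or otherwise the last earlier scheduled one. Enter transfusion up to that day as a covariate.
3. Leave the reference haemoglobin for the later outcomes as it is, as far as this point is concerned.

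The cost is wording only. The D1, D3 and D5 samples and the transfusion records are already planned, and neither care nor sample size changes. The small downside is that, in transfused patients, the exposure for the early outcome will differ from that of the primary analysis; the report should say so. If independence at discharge is really wanted, the alternative to item 1 is to add ADL to the end-of-hospitalisation assessment. That costs one six-item form per patient and helps only those not yet discharged.

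### The plan defines two haemoglobin exposures and does not say which one enters each model

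*Combined protocol and SAP*

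**What the plan says.** Section 2.1.2 (primary criterion) begins with "Haemoglobin level on day 5 post-operatively (considered the post-operative haemoglobin reference level in this study". For patients transfused post-operatively, "the reference haemoglobin level will be the haemoglobin level at the end of hospitalisation". It justifies day 5 by arguing that dehydration before surgery and haemodilution after it "cause the haemoglobin level to vary without there being any real deglobulation". Emergency-department, pre-operative and immediate post-operative values are therefore not used as the reference.

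Section 2.2.2 (secondary criteria) starts its list with another measure: "Lowest postoperative haemoglobin level recorded on admission to the emergency department, on admission to the ward, on D0 (day of surgery), D1, D3, D5, D10"; the time points end at D15. Severity classes follow, the worst being "less than 8 g/dL (and therefore requiring a transfusion". No rule is given for transfused patients.

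Section 5.2.1 relates loss of independence at 6 months to post-operative anaemia in a logistic model. The analyses of independence on day 5 (or at discharge), "at 1 and 3 months, and post-operative anaemia will be performed using the same method as for the primary endpoint". The Cox model for 6-month mortality refers simply to anaemia. The course from D0 to D15 is shown graphically. No model is tied to either haemoglobin measure, and none is said to use haemoglobin as a continuous variable or in classes.

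**The concern.** Sections 2.1.2 and 2.2.2 have the same layout: a haemoglobin measure first, then the outcomes. That suggests the lowest value is the exposure for the secondary outcomes. The study-wide wording in 2.1.2 suggests the opposite. Two competent analysts could fit different models from this text.

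Three things are at stake. First, estimates at months 1, 3 and 6 would be hard to compare if the exposure changed between them. Second, an unnamed exposure can be chosen after the results are known. Third, the lowest value as written has timing problems that the reference was partly designed to avoid. The 6-month model is not fully protected either: the primary objective concerns the severity of anaemia, and the only severity classes in the plan sit under the lowest value.

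**Working it through.** **1. The plan's own figures.** Section 5.2.2 gives 320 patients over 18 months (210 per year), 10% mortality, 10% loss to follow-up and 255 analysable.
- 320 × (1 − 0.10 − 0.10) = 256.0
- 210 × 1.5 × 0.9 × 0.9 = 255.15

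So 255 is reproduced. With 67.8% regaining independence (a 12-month figure used for planning), events ≈ 255 × 0.322 = 82, or about 8 model terms at 10 events each. Neither number depends on which haemoglobin measure is used. The form does matter to that budget: linear haemoglobin takes 1 term, four classes take 3.

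**2. The two measures side by side.**

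| | 2.1.2 reference | 2.2.2 lowest value |
|---|---|---|
| Sampling times | Day 5 | Emergency department, ward admission, D0, D1, D3, D5, D10, D15 |
| Transfused post-operatively | End-of-hospitalisation value | No rule |
| Classes | None stated | Four |
| Models in 5.2.1 that name it | None | None |

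**3. Timing, if the lowest value is used as written.**
- Two of its eight time points (emergency department and ward admission) are pre-operative, and 2.1.2 argues against such values as a reference.
- D10 and D15 come after the day-5 or discharge ADL, so the exposure can post-date that outcome.
- A patient who dies on D2 can contribute at most D0 and D1 of the six scheduled values from D0 to D15. A patient alive at D15 can contribute all six. In a Cox model the exposure then depends on surviving long enough to be sampled.

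**4. How far the measures can diverge.** The documents give no joint distribution, so this is an illustration on assumptions, with 200,000 simulated patients per scenario.
- Lowest value: normal, with 65% below 10 g/dL. Section 5.2.2 gives 65% for post-operative haemoglobin; applying it to the lowest value is an assumption. SD is 1.2 or 1.6 g/dL. Mean = 10 − SD × 0.385, i.e. 9.54 or 9.38.
- Transfused: everyone below 8 g/dL, plus 20% or 40% of those from 8 to 10. Section 2.1.2 says "it is generally accepted to transfuse patients with haemoglobin levels below 8 g/dL", with a threshold of 10 in some patients and discretion left to the prescriber.
- Reference = lowest value + a small recovery, |N(0.3, 0.4)| + the rise if transfused.

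Ranges below are over the four SD and transfusion-share combinations. In all of them, transfused patients average 1.4 to 2.3 g/dL lower than untransfused patients on the lowest value.

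| Rise (g/dL) | Transfused minus untransfused, reference value (g/dL) | Correlation of the two measures | Reference ≥ 8 among lowest < 8 |
|---|---|---|---|
| 0.5 | −1.8 to −0.9 | 0.95–0.97 | 59–76% |
| 1 | −1.3 to −0.4 | 0.89–0.95 | 78–92% |
| 1.5 | −0.8 to +0.1 | 0.78–0.89 | 89–98% |
| 2 | −0.3 to +0.6 | 0.64–0.80 | 95–99% |
| 3 | +0.7 to +1.6 | 0.34–0.56 | 99–100% |

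The second column is close to the gap on the lowest value plus the rise, for example −1.55 + 2 = +0.45. The order of the two groups reverses only when the rise exceeds the original gap.

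**The case against.** The best defence is that one exposure was always intended. Section 2.1.2 sets its reference for the study, 5.2.1 says the earlier time points follow the primary method, and the haemoglobin series in 2.2.2 could serve only the progression objective. This stands to the extent that no passage assigns the lowest value to any model. A reader might infer that the month-1, month-3 and mortality results do rest on a different exposure and cannot form a time course; the documents do not show that. They do not exclude it either. The reference to the same method follows a description of logistic regression and p < 0.20 selection, so it may mean only the statistical technique. One minimum per patient also cannot show progression, which the D0–D15 graph already covers.

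It is also fair that the 2.2.2 line may not mean a single minimum, because a lowest post-operative value cannot literally include two pre-operative points. That is a further reason to clarify it. Listing a second measure does not in itself contradict 2.1.2; the conflict arises only if that measure becomes the exposure.

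Three stronger readings are not supported:
- That the measures point in opposite directions in transfused patients. The sign depends on the rise.
- That the choice costs a known amount of power. Such figures depend on which measure is assumed to carry the true effect; the other is then attenuated.
- That the mortality association is biased towards the null by a known amount. The documents give no count of deaths before D5 or D15.

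Finally, using the 2.1.2 reference everywhere is not clean either. A patient who dies before day 5 has no day-5 value, and 5.2.4 allows no imputation. The end-of-stay value can follow the day-5 ADL. A patient discharged early has ADL recorded at discharge but haemoglobin prescribed for D5 (± 2 days, section 4.4). This objection stands and shapes the fix.

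**Conclusion.** The point holds as an unresolved exposure, not as a confirmed switch. Sections 2.1.2 and 2.2.2 define different haemoglobin measures, and 5.2.1 does not say which one, or in what form, enters each model. The two can rank transfused patients very differently: on the assumptions above the correlation is anywhere from 0.34 to 0.97, and most patients leave the below-8 class on the reference value in every scenario. The real divergence, and whether the order reverses, depends on the transfusion share and the post-transfusion rise, which the documents do not give. The simulation also takes the lowest value as preceding the reference and adds one fixed rise per transfused patient. The timing problems with the lowest value follow from the text alone, but apply only if it is used as the exposure. The plan should settle this before analysis.

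**What to change.** Amend 5.2.1, with a matching line in 2.2.2:
- **Months 1, 3 and 6:** name the 2.1.2 reference haemoglobin as the exposure and state whether it is continuous or in classes. If classes are used, restate them without overlap and in one unit; as printed they overlap and mix g/dL with g/L.
- **Day 5 or discharge:** use only haemoglobin taken on or before that ADL assessment.
- **Mortality:** start follow-up at the date of the exposure measurement (landmark) and report earlier deaths separately.
- **Sensitivity analysis:** keep the lowest value under that label, run identically at months 1, 3 and 6. Restrict it to post-operative samples up to D5, without emergency-department or ward-admission values. Include transfusion in the model, and do not claim independence from survival or treatment.
- **D10 and D15:** use them only for the progression graph, except where one is the end-of-hospitalisation value that 2.1.2 requires.

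The cost is wording plus one extra model at each of three time points. No new data are needed and the sample size is unchanged. The downsides are small: D10 and D15 no longer feed the severity class, and the mortality result becomes conditional on survival to the landmark.

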1. JUSTIFICATION FOR THE STUDY

1.1. POSITIONING OF THE RESEARCH

With the increase in life expectancy among the French population, there has been a rise in the number of patients with fractures of the upper femur (FESF), particularly among the elderly. In France, the number of hospital stays for UEF has been increasing by 0.3% per year since 1998, and the incidence remains predominantly female. The crude incidence rate of UEF was 42.1/10,000 for people over 55 years of age in 2007. UEF mainly affects elderly and very elderly people. There has been a gradual increase in the average age of fracture patients. Again in 2007, patients over 80 years of age accounted for 60% of male patients operated on for FESF and 70% of female patients (1). This is a serious condition, with the risk of death increasing with age. It is 2% in women under 80 during hospitalisation, rising to 8.3% in those over 95. This mortality rate is higher in men, reaching 15% in men over 94 during hospitalisation (1). Longer-term mortality rates vary according to studies, from 14.7% at one year (2) to 46% at one year in patients over 90 years of age (3). However, there has been a gradual decrease in this mortality rate in France, probably due to improved surgical and perioperative care for patients (4).

Anaemia is common in the geriatric population. In a survey of a hospitalised geriatric population, 24% of patients had anaemia, the aetiology of which was iron deficiency in 15% of cases (5). It is also common in surgery, particularly in the perioperative period. In a study of 546 patients with fractures of the upper femur, 40.4% had anaemia on admission and 93.0% had anaemia postoperatively (6).

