4. STUDY DESIGN AND PROCEDURE

4.1. STUDY SCHEDULE

The inclusion period will be 42 months. Follow-up is 6 months post-operative.

Patients may be included up to 48 hours after their arrival in the orthopaedic/orthopaedic surgery department.

a. D0 - Arrival in the orthopaedic/orthopaedic surgery department (after surgery)

Provision of the information leaflet and collection of non-objection after a reflection period.

Completion of the ASA score (*investigator*)

Biological tests (complete blood count (CBC), CRP, ferritin, transferrin saturation coefficient, albumin, vitamins B12, folate and vitamin D) (*investigator – performed on arrival at A&E or on admission to the department before surgery*)

Record of severe fractures prior to inclusion: upper end of the femur or humerus, proximal tibia, distal femur, 3 simultaneous ribs, wrist, pelvis and spine (Grio 2011 recommendations) (*investigator*)

Screening for previous or current upper function disorders (*investigator*)

Screening for major sensory disorders (*investigator*)

Completion of ADL and IADL questionnaires: **information relating to the week preceding the intervention** (*investigator: interview with patient, family or staff of residential care homes for elderly dependents (EHPAD)*)

Completion of the CIRS-G score (*investigator*)

Completion of the CAS questionnaire

Recording of lifestyle and living environment (*investigator*)

Number of medications (by class) taken by the patient on admission (anticoagulants, antiplatelet agents, NSAIDs, anti-osteoporotics, analgesics) (*investigator*) Completion of the MiniGDS score (*investigator*)

Collection of data on the procedure: time to surgery, type of fracture, surgical procedure, type of anaesthesia, weight-bearing authorisation, transfusion, number of red blood cell units received Haemoglobin measurement (if different from that taken in the emergency department or on admission to the ward before the procedure)

b. During the hospital stay: (trained orthopaedic nurses)

CAS score performed on days 1 to 3 post-operative, as well as on day 5 (or on discharge if this occurs before day 5)

Daily screening for confusion (CAM) until D10 if the patient is still hospitalised Completion of ADL questionnaires (*patient, family or nursing home resident interview*) on D5 post-operative (or on discharge if this occurs before D5)

Measurement of grip strength – Hand Grip on day 5 (or upon discharge if this occurs before day 5)

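### Secondary criteria (2.2.2): the haemoglobin severity bands do not form four classes, the post-operative nadir lists two pre-operative samples, and the composite loss outcome omits the protocol's own home-only limit on IADL

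*Combined protocol and SAP*

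**What the plan says.** All references are to the combined protocol and SAP.

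- **Severity bands (2.2.2).** Four classes are listed: above 12 g/dL; "less than or equal to 12 g/L"; "less than or equal to 8 g/L"; and below 8 g/dL.
- **Nadir (2.2.2).** The criterion is the "Lowest postoperative haemoglobin level recorded on admission to the emergency department, on admission to the ward", followed by D0, D1, D3, D5, D10 and D15. Section 2.1.2 groups values "recorded in A&E or on admission to the ward prior to surgery, or immediately post-operatively" as open to distortion by fluid status. Section 4.1(a) describes the admission blood tests as "performed on arrival at A&E or on admission to the department before surgery". It also asks for a D0 "Haemoglobin measurement (if different from that taken in the emergency department or on admission to the ward before the procedure".
- **Loss of independence.** Section 2.1.2 defines primary loss as a fall of at least one point in ADL. Section 2.2.2 defines secondary loss as such a fall in ADL, IADL or both, with no restriction by residence. Section 4.3(a) limits interpretation of IADL to people living at home. Section 5.2.1 analyses loss at day 5, month 1 and month 3 by the primary-endpoint method and names neither scale.
- **IADL scoring (4.3(a)).** There are four items, each coded 0, 0.5 or 1, and a stated range of 0 to 8.

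**The concern.** These are definitions that an analyst has to program, and followed literally they give wrong or conflicting results. The severity table would have a gap or a class that is almost empty. A value labelled as the post-operative minimum could come from before the operation. At months 1 and 3, a care-home resident could be counted as having lost independence because of an IADL fall that the protocol itself calls uninterpretable.

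The loss definition matters most, because it feeds a planned regression. Two analysts could both comply with the plan, one using ADL alone and the other the composite, and report different event rates at months 1 and 3. If the choice is left until results are visible, it becomes a choice of outcome.

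**Working it through.** **1. Bands.** Inputs: the four limits in 2.2.2. Assumed grid: haemoglobin 4.0 to 18.0 g/dL in steps of 0.1, which is 141 values.

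Units as printed (12 g/L = 1.2 g/dL; 8 g/L = 0.8 g/dL):
- below 8 g/dL: 7.9 and lower, 40 values;
- both g/L bands: no value on the grid;
- above 12 g/dL: 12.1 and higher, 60 values;
- no class: 8.0 to 12.0, 141 − 40 − 60 = 41 values.

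Two classes work, with a gap between them.

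All units read as g/dL:
- 4.0 to 7.9 meets three definitions (≤12, ≤8, <8);
- 8.0 meets two (≤12, ≤8);
- 8.1 to 12.0 meets one (≤12);
- 12.1 and higher meets one (>12).

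Assigning each value to its most severe class gives >12, 8.1 to 12.0, the single value 8.0, and <8. Three classes work; the fourth holds one value.

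**2. Nadir.** Section 2.2.2 lists eight sampling points. Sections 2.1.2 and 4.1(a) place two of them, emergency department and ward admission, before surgery. The other six run from D0 to D15. Section 4.1(a) heads D0 as arrival in the department after surgery, 4.4 ties D0 to the return from the procedure, and 5.2.1 states that "The progression of post-operative anaemia (D0 to D15) will be described graphically". D0 is therefore post-operative by the plan's own usage. Because of the conditional wording in 4.1(a), a separate D0 sample may not exist for every patient.

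On size, section 1.1 cites a study of 546 patients in which "40.4% had anaemia on admission and 93.0% had anaemia postoperatively". The difference, 93.0 − 40.4 = 52.6 percentage points, suggests that an admission value will seldom be the lowest. These are group prevalences, so they do not give the frequency of a pre-operative minimum.

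**3. Loss of independence.** Side by side:
- 2.2.2: composite, all patients; 4.3(a): IADL interpretable only at home.
- 3.3 does not exclude care-home residents; 4.3(e) lists a care home among the living arrangements.
- 2.2.2 and 4.3(a) schedule no IADL on day 5, so the composite cannot be formed there.
- 5.2.1 does not choose between the definitions in 2.1.2 and 2.2.2.

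Every ADL loss is also a composite loss, so the composite rate is equal to or higher than the ADL-only rate.

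A care-home resident changes class only if the IADL fall is at least 1 and the ADL fall is below 1. A resident whose pre-fracture IADL is below 1 cannot fall by 1. The documents do not give the care-home share. For each 10 percentage points of the 255 analysable patients in 5.2.2, 255 × 0.10 = 25.5, or about 26 residents, of whom only a subset can change class.

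**4. IADL range.** Maximum = 4 items × 1 = 4. Steps of 0.5 from 0 to 4 give 9 scores. A range of 0 to 8 implies 17, of which 17 − 9 = 8 cannot occur.

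**The case against.** The strongest reply is that most of this is editorial. The g/L units may be a translation or typing slip, 5.2.1 puts neither the bands nor the nadir in a model, and a true minimum will usually be post-operative anyway. All of that is fair and limits the weight of the first two items. It does not remove them: correcting the units leaves two cuts at 8, and the label and the sample list still disagree.

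On IADL, section 4.3(a) already states the home-only limit, which could be read as applying throughout. Collecting IADL from nursing-home staff is not the same as interpreting it, so there is no contradiction in collection. What stands is that 2.2.2 counts IADL falls without that limit, and no rule covers residents or patients who move into care after the fracture.

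A reader might infer more than the documents support:
- *That the primary endpoint is damaged*, because the primary objective speaks of severity and 2.2.2 holds the only severity classes. Section 2.1.2 names the haemoglobin level and ADL change as the primary criterion; the bands sit under the secondary criteria.
- *That D0 is pre-operative or undefined.* Sections 4.1(a), 4.4 and 5.2.1 treat it as post-operative.
- *That the nadir may post-date the day-5 outcome and so bias it.* No section plans an analysis of that pair.
- *That about 26 patients per 10 percentage points would be misclassified.* That figure is an upper limit.
- *That the composite must be replaced by ADL alone.* Section 2.2.2 chose the composite; keeping it and limiting its IADL part is the closer correction.

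**Conclusion.** The concern holds for the secondary criteria. The rules are wrong as written, not merely short of detail.

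- **Bands:** three of four classes work if every unit is g/dL; two work as printed, with 8.0 to 12.0 g/dL unclassified. The counts assume reporting to 0.1 g/dL. The documents do not show which cut-point was intended.
- **Nadir:** two of eight listed samples are pre-operative. The effect is probably small and cannot be quantified from the documents.
- **Loss of independence:** this item carries the weight. The definition is open at months 1 and 3, and the composite counts falls that the protocol says cannot be interpreted. The number reclassified is not derivable. The upper limit of about 26 per 10 percentage points uses 255, which 5.2.2 derives from 18 months at one hospital, whereas 4.1 and 4.2 describe 42 months and several centres; it scales with the number analysed.
- **IADL range:** if the item coding is right, no classification changes. If the range is right and the coding is not, the meaning of a one-point fall would need review.

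**What to change.** 1. Restate the severity classes in 2.2.2 as mutually exclusive, exhaustive bands in g/dL. The sponsor should supply or delete the duplicated cut-point.
2. Define the lowest post-operative haemoglobin from post-operative samples only. Count D0 only when a separate sample was taken after surgery.
3. State in 5.2.1 which loss definition applies at each visit: ADL only at day 5. If the composite is kept at months 1 and 3, count its IADL part only in patients living at home, with home status fixed at inclusion as the main rule, so that the analysis does not select on a post-fracture state. Report ADL-only loss alongside, and the number who have left home by each visit.
4. Reconcile the IADL range with the item coding.

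The cost is protocol and SAP wording before database lock. No new data are needed: living arrangements are already recorded at inclusion and at each call (4.1, 4.3(e)). The IADL part will cover fewer patients. Fixing status at inclusion also means that IADL still counts for patients who later move into care, where 4.3(a) would not interpret it. The ADL-only result and the count of movers let a reader judge how much that matters.
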